### **Regulatory Reporting Requirements for Serious Adverse Events**

If subject is permanently withdrawn from protocol-required therapies because of an SAE, this information must be submitted to the Sponsor.

Prompt notification by the investigator to the sponsor of SAEs is essential so that legal obligations and ethical responsibilities towards the safety of subjects and the safety of a study treatment under clinical investigation are met.

The sponsor has a legal responsibility to notify both the local regulatory authority and other regulatory agencies about the safety of a study treatment under clinical investigation. The Individual safety reports must be prepared for suspected unexpected serious adverse reactions according to local regulatory requirements and sponsor policy and forwarded to investigators as necessary.

An investigator who receives an individual safety report describing an SAE or other specific safety information (eg, summary or listing of SAEs) from the sponsor will file it along with the Investigator's Brochure and will notify the IRB/IEC, if appropriate according to local requirements.

Part B of the study - to comply with worldwide reporting regulations for SAEs, the treatment assignment of subjects who develop serious, unexpected, and related AEs may be unblinded

Approved

by Amgen before submission to regulatory authorities. Aggregate analyses may also be unblinded by the Safety Assessment Team, as appropriate. Investigators will receive notification of related SAE reports sent to regulatory authorities in accordance with local requirements.

## **Safety Monitoring Plan**

Subject safety will be routinely monitored as defined in the Sponsor's safety surveillance and signal management processes.

### **7.4.2. Clinical Laboratory Evaluations**

Blood and urine samples will be collected for clinical laboratory evaluations (including clinical chemistry, hematology, urinalysis, and serology) at the times indicated in the Schedule of Assessments in [Appendix 6](#). Clinical laboratory evaluations are listed in [Appendix 3](#).

Subjects will be asked to provide urine samples for drugs of abuse screen and cotinine test, and will undergo an alcohol breath test at the times indicated in the Schedule of Assessments in [Appendix 6](#). For all female subjects, a pregnancy test will be performed at the times indicated in the Schedule of Assessments in [Appendix 6](#).

The Investigator (or designee) is responsible for reviewing laboratory test results and recording any clinically relevant changes occurring during the study in the appropriate CRF. The Investigator (or designee) must determine whether an abnormal value in an individual study subject represents a clinically significant change from the subject's baseline values. In general, abnormal laboratory findings without clinical significance (based on the Investigator's [or designee's] judgment) are not to be recorded as AEs. However, laboratory value changes that require treatment or adjustment in current therapy are considered AEs. Where applicable, clinical sequelae (not the laboratory abnormality) are to be recorded as AEs.

### **7.4.3. Vital Signs**

Supine (or semi-recumbent) BP, supine (or semi-recumbent) pulse rate, and oral body temperature will be assessed at the times indicated in the Schedule of Assessments in [Appendix 6](#). Vital signs may also be performed at other times if judged to be clinically appropriate or if the ongoing review of the data suggests that a more detailed assessment of vital signs is required.

Vital signs measurements will be taken singly and will be repeated once if outside the relevant clinical reference range.

Subjects must be supine or semi-recumbent for at least 5 minutes before BP and pulse rate measurements.

### **7.4.4. Physical Examination**

A full physical examination and symptom-directed physical examination will be performed at the timepoints specified in the Schedule of Assessments in [Appendix 6](#).

## 8. SAMPLE SIZE AND DATA ANALYSIS

### 8.1. Determination of Sample Size

With approximately 60 enrolled subjects, it is estimated that approximately 48 evaluable subjects will have data from all 3 periods in Part B.

Based on the calculation of the sample size for a TQT study, assuming a 1-sided 5% significance level and a within-subject standard deviation (SD) of 7 msec for  $\Delta QTcF$ , and a true mean difference of 3 msec in  $\Delta QTcF$  between OM and placebo, a sample size of 48 evaluable subjects would be expected to provide 99.5% power to demonstrate that the upper bounds of all the 2-sided 90% confidence intervals (CIs) on  $\Delta\Delta QTcF$  will fall below 10 msec for up to 8 timepoints. With the within-subject SD of 8 msec and other similar assumptions, the power will decrease to 96.5%.

Determination of sample size for assay sensitivity:

Assuming a 1-sided 5% significance level and a within-subject SD of 7 msec for  $\Delta QTcF$ , a sample size of 48 evaluable subjects will provide a power of 99.9% to exclude a mean difference of 5 msec in  $\Delta QTcF$  between moxifloxacin and placebo groups from the lower bound of the 2-sided 90% CI on  $\Delta\Delta QTcF$  at at least 1 of the 3 prespecified timepoints. With the within-subject SD of 8 msec and other similar assumptions, the power will decrease to 99%.

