**Study design:**

This is a single-center, single-dose (Part A; PK Evaluation Period), and randomized, 3-period, 3-treatment, crossover, single-dose (Part B) study in healthy adult subjects to determine whether OM prolongs the QTc after a single oral dose administration of 50 mg OM. Treatment in Part A will consist of a single 25-mg OM treatment (Treatment 1). Subjects whose resulting maximum observed plasma OM concentration ( $C_{max}$ ) is  $\leq 350$  ng/mL will be randomized into Part B, which consists of 3 periods wherein a single treatment is given in each period. Treatments will consist of placebo (Treatment A), OM 50 mg (Treatment B), or moxifloxacin 400 mg (Treatment C). All treatments (Part A and Part B) will be separated by a washout of at least 7 days.

Part A

All subjects will receive Treatment 1. OM treatment will be open-label. Safety and tolerability monitoring will be conducted throughout Part A, and blood samples will be collected to determine plasma OM concentrations. Safety digital ECG recordings will be reviewed by the Investigator or designee on Day -1, and on Day 1 at the following timepoints: predose and at 1, 4, 24, 48, and 120 hours postdose. Pharmacokinetic blood samples for OM will be collected at the following timepoints on Day 1: predose and 0.25, 0.5, 0.75, 1, 2, 3, 4, 6, 8, and 12 hours postdose.

Subjects whose resulting  $C_{max}$  is  $\leq 350$  ng/mL will be randomized into Part B. There will be a minimum of a 7-day washout between treatments in Part A and Part B.

Part B

After completing Part A, eligible subjects will be randomized to receive 3 treatments in 1 of 6 sequences, as follows:

Approved

Approved

Sequence	Period	Period	Period	
	1	2	3	
1	A	B	C	
2	B	C	A	
3	C	A	B	
4	A	C	B	
5	C	B	A	
6	B	A	C	

In Part B, placebo and OM treatments will be double-blinded, moxifloxacin treatment will be open-label, and the core ECG lab will be blinded to all treatment information. Safety and tolerability monitoring will be conducted throughout the study, and blood samples will be collected to determine plasma OM and moxifloxacin concentrations in relevant periods.

In each Part B treatment period, continuous digital ECG recording will be performed for approximately 27 hours, from predose through at least 24 hours postdose, and up to 10 replicate 12-lead ECGs will be extracted at the following timepoints on Day 1: -1.25, -1, and -0.75 hours predose and 0.25, 0.5, 0.75, 1, 1.5, 2, 3, 4, 8, 12, and 24 hours postdose.

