#### **8.3.3.1. Baseline for Cardiodynamic ECG Assessments**

For all continuous ECG parameters from each period, baseline will be the average of the measured ECG intervals from the 3 predose timepoints (-1.25, -1, and -0.75 hours) for the respective period.

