#### **8.3.3.2. Primary Cardiodynamic Analysis**

The primary analysis of the QT/QTc data will be the “by-timepoint” analysis for QTcF, based on a linear mixed-effects model with  $\Delta$ QTcF as the dependent variable; period, sequence, time (categorical), treatment (OM, moxifloxacin, and placebo), and time-by-treatment interaction as fixed effects; and baseline QTcF as a covariate. An unstructured covariance matrix will be specified for the repeated measures at timepoints for subject within-treatment period. If the model with an unstructured covariance matrix fails to converge, other covariance matrices such as compound symmetry and autoregressive will be considered. The model will also include a subject-specific random effect. If the fixed effects for period and/or sequence should prove to be nonsignificant (ie, if the p-value > 0.1), these effects may be removed from the model and the analysis will be repeated without those covariates. From this analysis, the least squares (LS) mean and 2-sided 90% CI will be calculated for the contrast “OM versus placebo” at each postdose timepoint, separately. If the upper bound of the CI lies below 10 msec for all postdose timepoints, OM will be concluded not to have a significant effect on QT interval prolongation.

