# 4 Cardiodynamic ECG Assessment

## 4.1 ECG and PK Sample Collection

In Part B, continuous 12-lead digital ECG recording will be performed on Day 1 of each treatment period. The recording will be performed for approximately 27 hours in total. Subjects should lie down in a quiet room for at least 10 minutes before and 5 minutes after each extraction at the time points listed. Digital 12-lead ECGs will be extracted in up to 10 replicates at -1.25, -1, and -0.75 hours predose and at 0.25, 0.5, 0.75, 1, 1.5, 2, 3, 4, 8, 12, 24 hours postdose.

The Investigator site will utilize their Mortara Surveyor system. The continuous 12-lead digital ECG data will be stored onto SD memory cards. The ECGs to be used in the analyses will be read centrally by ERT.

The following principles will be followed in ERT's core laboratory:

• ECG analysts are blinded to the subject, visit, and treatment allocation.

• Baseline and on-treatment ECGs for a particular subject will be over-read on the same lead and will be analyzed by the same reader.

ECG intervals will be measured by the core laboratory in a blinded manner using the Expert Precision QT technique (see Appendix A for more details). The ECG database will be locked before any statistical analysis is undertaken.

Blood samples for PK determination will be drawn at the same time points as ECGs (i.e., predose and at 0.25, 0.5, 0.75, 1, 1.5, 2, 3, 4, 8, 12, 24 hours postdose) and additionally at 48, 72, 96, 120 hours postdose. PK samples should be collected within 5 minutes after the completion of the digital ECG extraction window through 24 hours postdose and within  $\pm$  2 hours of the digital ECG extraction windows after 24 hours postdose.

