# 6 Analysis

## 6.1 By-Time Point Analysis (Primary Analysis)

The primary analysis of the QT/QTc data will be the "by-time point" analysis for QTcF, based on a linear mixed-effects model with  $\Delta$ QTcF as the dependent variable; period, sequence, time (categorical), treatment (OM, moxifloxacin, and placebo), and time-by-treatment interaction as fixed effects; and baseline QTcF as a covariate. An unstructured covariance matrix will be specified for the repeated measures at time points for subject within treatment period. If the model with an unstructured covariance matrix fails to converge, other covariance matrices such as compound symmetry and autoregressive will be considered. The model will also include a subject-specific random effect. If the fixed effects for period and/or sequence should prove to be not significant (i.e., if the P value > 0.1), these effects may be

removed from the model and the analysis will be repeated without those covariates. From this analysis, the least squares (LS) mean, SE, and 2-sided 90% CI will be calculated for the contrast "OM versus placebo" at each postdose time point, separately. If the upper bound of the CI of  $\Delta\Delta$ QTcF lies below 10 ms for all postdose time points, OM will be concluded not to have a significant effect on QT interval prolongation.

The SAS code for the by-time point analysis for QTcF is as follows.

PROC MIXED DATA=ECG; CLASS SUBJID TREAT TIME PERIOD SEQUENCE; MODEL DQTC=BASE TREAT TIME TREAT\*TIME PERIOD SEQUENCE/DDFM=KR; random intercept / SUBJECT = SUBJID type=UN; REPEATED TIME / SUBJECT = PERIOD\*SUBJID type = un; LSMEANS TREAT\*TIME/CL DIFF ALPHA=0.1; RUN;

Where ECG=QT/QTc analysis set, SUBJID=subject identifier, TREAT=treatment (OM, moxifloxacin, and placebo), TIME=nominal time point, BASE= baseline QTcF, PERIOD=period, SEQUENCE=sequence, and DQTC=ΔQTcF.

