## **6.4** Determination of Sample Size

With approximately 60 enrolled subjects, it is estimated that approximately 48 evaluable subjects will have data from all 3 periods in Part B.

Based on the calculation of the sample size for a TQT study, assuming a 1-sided 5% significance level and a within-subject SD of 7 ms for  $\Delta$ QTcF, and a true mean difference of 3 ms in  $\Delta$ QTcF between OM and placebo, a sample size of 48 evaluable subjects would be expected to provide 99.5% power to demonstrate that the upper bounds of all the 2-sided 90% CIs on  $\Delta\Delta$ QTcF will fall below 10 ms for up to 8 time points. With the within-subject SD of 8 ms and other similar assumptions, the power will decrease to 96.5%.

Determination of sample size for assay sensitivity

Assuming a 1-sided 5% significance level and a within-subject SD of 7 ms for  $\Delta QTcF$ , a sample size of 48 evaluable subjects will provide a power of 99.9% to exclude a mean difference of 5 ms in  $\Delta QTcF$  between moxifloxacin and placebo groups from the lower bound of the 2-sided 90% CI on  $\Delta\Delta QTcF$  at at least 1 of the 3 prespecified time points. With the within-subject SD of 8 ms and other similar assumptions, the power will decrease to 99%.

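### The primary power is stated for at most 8 timepoints, but the primary decision rule covers all 11 scheduled postdose timepoints

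*Protocol*

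**What the plan says.** Protocol 8.1 bases the primary power on 48 evaluable subjects, "assuming a 1-sided 5% significance level and a within-subject standard deviation (SD) of 7 msec", and a true OM-minus-placebo difference of 3 ms. It states 99.5% power that the upper bounds of the two-sided 90% intervals "will fall below 10 msec for up to 8 timepoints". For an SD of 8 ms it gives 96.5%. SAP 6.4 repeats the statement with the same count: "will fall below 10 ms for up to 8 time points".

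The synopsis of the protocol lists the postdose ECG extractions as "0.25, 0.5, 0.75, 1, 1.5, 2, 3, 4, 8, 12, and 24 hours postdose". SAP 4.1 has the same list: "0.25, 0.5, 0.75, 1, 1.5, 2, 3, 4, 8, 12, 24 hours postdose". That is 11 timepoints.

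The decision rule in Protocol 8.3.3.2 reads "If the upper bound of the CI lies below 10 msec for all postdose timepoints". SAP 6.1 likewise asks that the bound "lies below 10 ms for all postdose time points". The SAS code in SAP 6.1 fits the treatment-by-time interaction over the nominal times without selecting a subset.

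**The concern.** An all-timepoints rule becomes harder to pass as timepoints are added, because each is another chance for an upper bound to reach 10 ms. Power quoted for up to 8 therefore does not cover a rule applied to 11.

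Neither document names 8 timepoints for the primary test, and neither gives power for 11. Where the authors intend a subset they say so: assay sensitivity is confined to 2, 3 and 4 hours (Protocol 8.3.3.4, SAP 6.1.2), and its power statement refers to 3 prespecified timepoints.

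At stake is whether the sample-size justification matches the prespecified primary test. If it does not, a reader may ask which 8 timepoints were meant, an awkward question for a rule that applies to all of them.

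**Working it through.** **Inputs.** From Protocol 8.1 and SAP 6.4: N = 48 evaluable, one-sided 5% level, margin 10 ms, true difference 3 ms, within-subject SD 7 or 8 ms. From Protocol 8.3.3.2 and SAP 6.1: success is required at every postdose timepoint. From the schedule: k = 11.

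**Standard error.** For a within-subject treatment difference, SE = SD × √(2/48):

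- SD 7: 7 × 0.2041 = 1.429 ms
- SD 8: 8 × 0.2041 = 1.633 ms

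**Power at one timepoint.** The distance to the margin is 10 − 3 = 7 ms. Under the normal approximation, power = Φ(7/SE − 1.645):

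- SD 7: Φ(4.899 − 1.645) = Φ(3.254) = 0.99943
- SD 8: Φ(4.287 − 1.645) = Φ(2.642) = 0.99588

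The noncentral t gives 0.99936 and 0.99548 with 94 df (47 × 2, three-treatment crossover), and 0.99927 and 0.99505 with 47 df (paired difference).

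**Power at k timepoints.** With independent timepoints and a 3 ms difference at each, joint power is the single-timepoint power raised to k.

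| Method | SD 7, k = 8 | SD 7, k = 11 | SD 8, k = 8 | SD 8, k = 11 |
|---|---|---|---|---|
| Stated in the plan | 99.5% | none | 96.5% | none |
| Normal | 99.55% | 99.38% | 96.75% | 95.56% |
| t, 94 df | 99.49% | 99.29% | 96.44% | 95.14% |
| t, 47 df | 99.42% | 99.20% | 96.10% | 94.68% |

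The k = 8 columns come close to both printed values. Independence is inferred from that match; the documents do not state it. Reading the SD as that of the paired difference would instead give more than 99.99% at k = 8, which does not fit.

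Moving from 8 to 11 costs 99.49 − 99.29 = 0.20 points at SD 7 (94 df; about 0.2 under each method). At SD 8 it costs 96.75 − 95.56 = 1.19 (normal), 96.44 − 95.14 = 1.30 (94 df) or 96.10 − 94.68 = 1.42 (47 df).

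**Correlated timepoints.** Protocol 8.3.3.1 says "baseline will be the average of the measured ECG intervals from the 3 predose timepoints" for the period, so every change in a period shares one baseline and positive correlation is plausible. The documents give no value, so those below are assumptions (equal correlation between all pairs). Power for k = 11:

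| Assumed correlation | SD 7, normal | SD 7, paired t | SD 8, normal | SD 8, paired t |
|---|---|---|---|---|
| 0 | 99.38% | 99.2% | 95.56% | 94.7% |
| 0.3 | 99.40% | 99.2% | 96.06% | 95.3% |
| 0.5 | 99.47% | 99.3% | 96.71% | 96.0% |
| 0.7 | 99.59% | 99.4% | 97.57% | 97.0% |

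The paired-t columns are simulated (48 subjects, 47 df, 40,000 runs, Monte Carlo error about 0.1 point). Like for like, at correlation 0.5 and SD 8 under the normal approximation, power is 97.43% for 8 timepoints and 96.71% for 11, a cost of 0.7 points.

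**The case against.** The best defence is that the sentence is conditional and correct on its own terms: it speaks of up to 8 timepoints, and its figures hold for 8. This stands, and it means the fault is one of scope, not calculation. It does not rescue the statement, because 11 exceeds 8 and the rule being powered covers 11.

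A second argument is that the loss depends on two severe assumptions. One is independence. At an assumed correlation of 0.5, 11-timepoint power at SD 8 is 96.7% by the normal approximation, above the printed 96.5%, although the paired-t figure is 96.0%. The other is a 3 ms effect at every timepoint. Protocol 1.2.2 puts tmax at about 0.5 hours and the half-life at about 21 hours, so a constant effect would be a worst case if the effect follows concentration. If it were 3 ms at 8 timepoints and 0 to 2 ms at the other 3, independent-timepoint power at SD 8 would be 96.75–96.58% (normal) or 96.44–96.26% (94 df), essentially the printed value. So the printed figures need not overstate the true power by much, or at all. But neither document states a correlation or an effect-time profile. If the sponsor relied on either, the text should say so.

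Third, the cited sample-size method cannot be checked from these documents, and no variant tried returns exactly 96.5%. The sponsor may therefore prefer figures from its own calculation. That is reasonable, provided they refer to 11 timepoints.

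Finally, nothing in the conduct or conclusions of the trial turns on this. That is agreed, and it is why the point is minor.

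**Conclusion.** The concern holds, as a minor point. Both sample-size sections give power for at most 8 timepoints, while both decision rules apply to the 11 scheduled, so the plan contains no power figure for its own primary test.

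On the plan's inputs, assuming independent timepoints and a true 3 ms difference at each, power for the actual rule is about 99.3% at SD 7 (99.2–99.4% across methods) and about 95% at SD 8 (94.7–95.6%). Positive correlation would raise these figures. At SD 7, power stays between 99.2% and 99.6% across the correlations examined. The sample of 48 evaluable subjects remains adequate throughout.

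**What to change.** In Protocol 8.1 and SAP 6.4, change the count to all 11 postdose timepoints and restate the power with its assumptions. For example:

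> Power is about 99.3% (within-subject SD 7 msec) and about 95% (SD 8 msec) for all 11 postdose timepoints, assuming independent timepoints and a true difference of 3 msec at every timepoint; these figures are conservative if timepoints are positively correlated.

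If the sponsor prefers its own method, it should rerun it for 11 timepoints and state any correlation or effect profile it uses. The cost is one sentence in each document and a slightly lower stated power. Sample size and analysis need no change.

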### **1.2.3. Non-Amgen Non-Investigational Product Background: Moxifloxacin**

Moxifloxacin is a broad-spectrum fluoroquinolone antibiotic that binds to and inhibits the hERG IKr  $\alpha$  subunit and causes a mean increase of the QTc interval of 6 ms after a single 400-mg oral dose. Moxifloxacin is commonly used as a positive control in thorough QT (TQT) studies to satisfy the requirements of ICH E14.

Refer to the regional manufacturer package insert of AVELOX (moxifloxacin hydrochloride) tablets for additional information.

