### 3.2. Discussion of Study Design

The purpose of this study is to evaluate the potential for OM to cause QT prolongation. As OM exposure affects cardiac contractility, the primary endpoint for this study will be the QTcF. A supratherapeutic dose of OM is unable to be administered due to the step-wise titration scheme needed to optimize OM dose and safety concerns in healthy subjects. A

crossover design has been selected, with subjects acting as their own controls to minimize inter-subject variability.

This study will be double-blinded for OM and placebo to control for bias in safety assessments, including safety ECGs, and open-label for moxifloxacin as the QTc effects and AEs of this drug are well characterized. The central ECG laboratory and ECG readers will be blinded to treatment sequence, timepoint, and subject.

The anticipated  $C_{max}$  resulting from the 50-mg OM dose used for the assessment of QTc effects will be consistent with that in Phase 3 and will be below 1200 ng/mL. However, to provide further assurance that subjects will not exceed 1200 ng/mL, this study incorporates an initial PK assessment at 25 mg to confirm that individual  $C_{max}$  values do not exceed 350 ng/mL; given the linear PK of OM, a subject with  $C_{max} \leq 350$  ng/mL at 25 mg would be expected to have predicted exposure no higher than 700 ng/mL at 50 mg, and therefore below 1200 ng/mL.

This study will be conducted using healthy subjects to eliminate potential variables known to have an effect on ECG parameters (eg, concomitant drugs, diseases). Subjects will be randomized to treatment in an effort to ensure that baseline characteristics are evenly distributed across treatment sequences. The sample size in this study is driven by the need to perform a by-timepoint statistical analysis of the primary endpoint per the ICH E14 guidance.

Moxifloxacin will be included as a positive control to validate the sensitivity of the assay to detect small increases from baseline in QTc. Following single oral doses of 400 mg moxifloxacin, a QTc increase of 6 ms has occurred at  $t_{max}$ . Moxifloxacin plasma samples will be collected and concentrations may be measured, but PK vs QTc modeling will not be performed, as the QT effects of moxifloxacin are well-known.

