### 3.3. Selection of Doses in the Study

According to ICH E14, the highest therapeutic dose and a supratherapeutic dose are recommended for the QT/QTc study. The OM dose in ongoing Phase 3 studies is individualized using a PK-based titration to avoid excessive OM exposures ( $> 1200$  ng/mL). The observed mean (standard deviation; SD) steady state  $C_{max}$  from a Phase 2 study (20110151) for 25 mg BID and 50 mg BID are 193 (58.5) ng/mL and 492 (115) ng/mL, respectively. A supratherapeutic dose will not be evaluated due to the identified risk of myocardial ischemia or infarction.

Based on Study 20160159, the 25-mg oral solution formulation resulted in a mean (SD)  $C_{max}$  of 220 (71.2) ng/mL after a single dose administration in healthy subjects. This exposure is well below the 1200 ng/mL threshold and the dose is proximal to the 50-mg dose, such that it is anticipated to provide a very reliable prediction of the  $C_{max}$  of 50 mg, given the linear PK of OM.

In Part B, OM treatment will be a 50-mg single dose of oral solution. The 50-mg oral solution dose should achieve therapeutic concentrations (range of 300 to 700 ng/mL). Moxifloxacin 400 mg is associated with an observed 6 ms increase in the mean placebo- and baseline-corrected QTc interval, which is within the range required by ICH.

In summary, to attain clinically relevant concentrations, a single dose of 50 mg oral solution will be administered for the purpose of evaluating the proarrhythmic potential of OM as reflected by change in the QTc interval in healthy subjects.

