#### **8.3.3.4. Assay Sensitivity**

The analysis to show assay sensitivity will be based on the change-from-baseline post-dosing QTcF of moxifloxacin. The same model will be used as described for the primary analysis. For the timepoints 2, 3, and 4 hours after dose administration, the contrast in treatment  $\Delta\Delta\text{QTcF}$  = “moxifloxacin – placebo” will be tested against the 1-sided null hypothesis  $\Delta\Delta\text{QTcF} \leq 5$  msec at the 5% level. Multiplicity will be controlled using the Hochberg procedure. If after this procedure QTc ( $\Delta\Delta\text{QTcF}$ ) is significantly larger than 5 msec for at least 1 timepoint, assay sensitivity will be considered shown. In addition, 2-sided 90% CIs will be obtained for the contrast at all timepoints and used in the figures.

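### A negative QT conclusion for OM does not require assay sensitivity, and the stated assay-sensitivity power omits its moxifloxacin effect and cannot be reached at the cited 6 ms

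*Protocol*

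**What the plan says.** **Decision rule.** Protocol 8.3.3.2 reads: "If the upper bound of the CI lies below 10 msec for all postdose timepoints, OM will be concluded not to have a significant effect". SAP 6.1 has the same rule: the upper bound "lies below 10 ms for all postdose time points, OM will be concluded not to have a significant effect on QT interval prolongation". Neither adds a second condition.

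**Positive control.** Protocol 3.2 gives its purpose: "Moxifloxacin will be included as a positive control to validate the sensitivity of the assay to detect small increases from baseline in QTc". Protocol 8.3.3.4 and SAP 6.1.2 test moxifloxacin minus placebo against 5 ms at 2, 3 and 4 h, one-sided at 5%. "Multiplicity will be controlled using the Hochberg procedure", and one significant timepoint is enough. Neither section says what follows if none is significant.

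**Power.** Protocol 8.1 states that "a sample size of 48 evaluable subjects will provide a power of 99.9% to exclude a mean difference of 5 msec in" ΔQTcF at one or more of the three timepoints, with a within-subject SD of 7 ms, and 99% with an SD of 8 ms. SAP 6.4 repeats this. No moxifloxacin effect is given, although the OM calculation just above it states its own (3 ms).

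**Moxifloxacin effect cited elsewhere.** Protocol 1.2.3: it "causes a mean increase of the QTc interval of 6 ms after a single 400-mg oral dose". Protocol 3.2: "a QTc increase of 6 ms has occurred at" tmax. Protocol 3.3: "Moxifloxacin 400 mg is associated with an observed 6 ms increase in the mean placebo- and baseline-corrected QTc interval".

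**The concern.** There are two linked defects.

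First, the OM conclusion is not tied to the control that is meant to validate it. If moxifloxacin fails its test, small OM differences could mean either no drug effect or an assay unable to see one. The written rule still returns a negative conclusion. The failure would be reported, but it would have no prespecified consequence.

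Second, the power that would reassure a reader that this will not happen cannot be checked, because its key input is missing. The one effect size in the documents lies only 1 ms above the 5 ms threshold, which is hard to square with a power of 99.9%.

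**Working it through.** **Inputs.** Protocol 8.1: n = 48 evaluable, within-subject SD 7 or 8 ms, one-sided 5%, OM true difference 3 ms, margin 10 ms, up to 8 timepoints. Protocol 8.3.3.4: threshold 5 ms, three timepoints, Hochberg. Protocol 1.2.3, 3.2 and 3.3: moxifloxacin 6 ms. Assumptions made here: the same true moxifloxacin effect at 2, 3 and 4 h, and a correlation between timepoints of 0 to 0.8 (the documents give none).

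**Standard error of a treatment difference.** SE = SD × √(2/48), which is 1.429 ms at SD 7 and 1.633 ms at SD 8.

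**Step 1: reproduce the OM power.** Per-timepoint power is Φ((10 − 3)/SE − 1.645).
- SD 7: Φ(4.90 − 1.645) = 0.9994. Eight independent timepoints: 0.9994^8 ≈ 99.5% (stated 99.5%).
- SD 8: Φ(4.29 − 1.645) = 0.9959. Eight timepoints: about 96.7%, or 96.4% with a t distribution on 94 df (stated 96.5%).

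So this standard error matches the plan's own calculation.

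**Step 2: the same model for moxifloxacin at 6 ms.** Per-timepoint power without adjustment is Φ((6 − 5)/SE − 1.645).
- SD 7: Φ(0.70 − 1.645) = 0.172. At least one of three, independent: 1 − 0.828³ ≈ 43%.
- SD 8: Φ(0.61 − 1.645) = 0.151. At least one of three, independent: 1 − 0.849³ ≈ 39%.

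Hochberg rejects at least one hypothesis if the largest p is ≤ 0.05, or the second largest ≤ 0.025, or the smallest ≤ 0.0167. Results by simulation (400,000 draws):

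| Test | SD | corr. 0 | corr. 0.5 | corr. 0.8 | Stated |
|---|---|---|---|---|---|
| Hochberg | 7 | 21.3% | 17.8% | 14.8% | 99.9% |
| Hochberg | 8 | 18.3% | 15.4% | 12.8% | 99% |
| Unadjusted 90% CI | 7 | 43.1% | 34.3% | 27.7% | 99.9% |
| Unadjusted 90% CI | 8 | 38.8% | 31.0% | 24.8% | 99% |

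Using one shared variance estimate lowers the correlation-0.8 Hochberg values to 14.0% and 12.2%, and the unadjusted SD 7 value to 26.9%. The most lenient reading treats 7 or 8 ms as the SD of the paired difference, with no adjustment and independent timepoints. It reaches 59% and 52%.

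**Step 3: what effect would give the stated powers?** Solving for 99.9% at SD 7 / 99% at SD 8:

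| Test | corr. 0 | corr. 0.5 | corr. 0.8 |
|---|---|---|---|
| Hochberg | 9.8 / 9.7 ms | 11.0 / 10.8 ms | 11.6 / 11.4 ms |
| Unadjusted 90% CI | 9.2 / 9.0 ms | 10.3 / 10.0 ms | 11.0 / 10.7 ms |

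The two stated powers agree with each other, but only at an effect well above 6 ms.

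**Step 4: probability that OM is declared negative while assay sensitivity is not shown.** Joint simulation with a shared placebo, OM at 3 ms, all 11 postdose timepoints and 100,000 draws:

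| True moxifloxacin effect | SD 7, corr. 0 / 0.5 / 0.8 | SD 8, corr. 0 / 0.5 / 0.8 |
|---|---|---|
| 6 ms | 78.1 / 81.9 / 84.9% | 78.1 / 82.4 / 86.0% |
| 8 ms | 12.9 / 25.2 / 33.4% | 21.8 / 35.2 / 43.9% |
| 10 ms | 0.1 / 1.1 / 2.9% | 0.5 / 3.7 / 7.5% |
| 11 ms | at most 1.8% | at most 1.8% |

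**The case against.** The rule is silent on a failed control; it does not say that OM passes regardless. Assay sensitivity is a stated secondary objective with a prespecified test, named timepoints, multiplicity control and its own table (14.1.5), so a failure could not be hidden. Adding the link changes no estimate, test or dataset.

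On power, the stated figures are not arithmetically wrong. A single effect of about 9.8 ms at independent timepoints gives both under Hochberg. The 6 ms appears only as background and in the design and dose rationale, never as a design value, and the documents do not show how it relates to a least-squares mean at 2 to 4 h. At the effect the sponsor presumably used, the stated power itself limits control failure to 0.1% (SD 7) or 1% (SD 8). The large joint probabilities belong to 6 ms only.

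Much of this stands. The power defect is an unreported input that conflicts with the cited figure, not a miscalculation, and the likelihood of the bad outcome depends on the true effect. None of it supplies the missing condition or the missing input. A reader might discount an OM result from a failed assay, but that would be judgement after the fact. The written rule gives the opposite answer.

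**Conclusion.** The concern holds. The decision rule is the more serious part and does not depend on the moxifloxacin effect: applied as written, a study that fails its positive control still meets the criterion for a negative QT conclusion.

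The power statement is a lesser but real defect. It omits the assumed effect, does not say whether it refers to the Hochberg test or to unadjusted intervals, and cannot be reconciled with 6 ms under any variant tried. The size depends on the true moxifloxacin effect: failure of the control alongside a negative OM result is the expected outcome at 6 ms and rare at 11 ms. These figures rest on 48 evaluable subjects, equal moxifloxacin effects at the three timepoints and the assumed correlation range.

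**What to change.** 1. In Protocol 8.3.3.2 and SAP 6.1, allow the negative OM conclusion only if every upper bound is below 10 ms **and** assay sensitivity is shown under Protocol 8.3.3.4 / SAP 6.1.2.
2. In Protocol 8.1 and SAP 6.4, state the assumed moxifloxacin effect at 2, 3 and 4 h and the assumed correlation between timepoints, and restate power under Hochberg for SD 7 and SD 8.
3. Either reconcile that effect with the 6 ms in Protocol 1.2.3, 3.2 and 3.3, or also report the power at 6 ms.

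The cost is one clause in each decision rule and a few sentences in each sample-size section, with no added subjects, data or tests. The price is that a negative OM conclusion then depends on the control succeeding, and the restated power may look less favourable.
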